## Safety of Cetuximab in Clinical Trials in Patients with Head and Neck Cancer

Except where indicated, the data described below reflect exposure to cetuximab in 208 patients with locally or regionally advanced SCCHN who received cetuximab in combination with radiation. Cetuximab was administered as monotherapy in 103 patients with recurrent or metastatic SCCHN. Of the 103 patients receiving cetuximab monotherapy, 53 continued to a second phase with the combination of cetuximab plus chemotherapy. Patients receiving cetuximab plus radiation therapy received a median of 8 doses (range 1-11 infusions). The population had a median age of 56; 81% were male and 84% Caucasian. Patients receiving cetuximab monotherapy received a median of 11 doses (range 1-45 infusions). The population had a median age of 57; 82% were male and 100% Caucasian. The most **serious adverse reactions** associated with cetuximab in combination with radiation therapy in patients with head and neck cancer were:

- Infusion reaction (3%)
- Cardiopulmonary arrest (2%)
- Dermatologic toxicity (2.5%)
- Mucositis (6%)
- Radiation dermatitis (3%)
- Confusion (2%)
- Diarrhea (2%)

Fourteen (7%) patients receiving cetuximab plus radiation therapy and 5 (5%) patients receiving cetuximab monotherapy discontinued treatment primarily because of adverse events.

The most common adverse events seen in 208 patients receiving cetuximab in combination with radiation therapy were acneform rash (87%), mucositis (86%), radiation dermatitis (86%), weight loss (84%), xerostomia (72%), dysphagia (65%), asthenia (56%), nausea (49%), constipation (35%), and vomiting (29%).

The most common adverse events seen in 103 patients receiving cetuximab monotherapy were acneform rash (76%), asthenia (45%), pain (28%), fever (27%), and weight loss (27%).

The data in the table below are based on the experience of 208 patients with locoregionally advanced SCCHN treated with cetuximab plus radiation therapy compared to 212 patients treated with radiation therapy alone.

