## 5. TREATMENT PLAN

- Loading dose of cetuximab 400 mg/m^2 IV over 120 minutes 2 weeks prior to starting radiation.
- Cetuximab 250 mg/m^2 IV over 60 minutes weekly, the week prior and during days of radiation, until radiation is completed (diphenhydramine hydrochloride [Benadryl] premedication 30-60 minutes prior to cetuximab infusion as required, see 5.1).
- Intratumoral EGFR AS injections weekly x 7 weeks (or less if there is no identifiable tumor), starting 2 weeks prior to radiation and after cetuximab is administered. Subsequent EGFR AS injections can be given before or after cetuximab is administered. Injections will be in the primary and/or lymph nodes. One site will be injected per weekly session. The intratumoral EGFR AS injections should occur during the same calendar day due to CTRC scheduling. If it is necessary the antisense injection can be scheduled within 1 business day of the original schedule date and then resume the original schedule.
- EGFR AS will be administered by direct intratumoral injection using direct visualization, endoscopy, or imaging-guidance (ultrasound) as clinically determined. The same lesion (primary tumor or lymph node) will be injected during treatment.
- Radiation therapy 70 Gy, 200 cGy/daily, 5 days/week (see 5.3). Radiation will start on a Monday, Tuesday, or Wednesday. Cetuximab will be given prior to radiation.
- A tumor biopsy will be performed prior to starting cetuximab and 2 weeks later but prior to starting radiation.
- In the first stage, after three (3) subjects are enrolled and have received all EGFR AS injections, there will be a two-week waiting period to assess adverse events before enrolling additional subjects. After the two-week period, additional subjects may be enrolled.

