### 7.2 Management of Infusion Reactions

Severe infusion reactions require the immediate interruption of cetuximab therapy and permanent discontinuation from further treatment. Appropriate medical therapy including epinephrine, corticosteroids, intravenous antihistamines, bronchodilators, and oxygen should be available for use in the treatment of such reactions. Patients should be carefully observed until the complete resolution of all signs and symptoms.

In clinical trials, mild to moderate infusion reactions were managed by slowing the infusion rate of cetuximab and by continued use of antihistamine pre-medications (e.g., diphenhydramine hydrochloride [Benadryl]) in subsequent doses. If the patient experiences a mild or moderate (Grade 1 or 2) infusion reaction, the infusion rate should be permanently reduced by 50%. For

grade 1 or 2 reactions manifesting only as delayed drug fever, see below.

Cetuximab should be immediately and permanently discontinued in patients who experience severe (Grade 3 or 4) infusion reactions.

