### 7.8 Duration of Therapy/Withdrawal from Study

Criteria for removal from study are:

- Disease progression,
- Study closure,
- Unacceptable adverse event(s) as defined in dose modification or other unacceptable AEs,
- Patient decision to withdraw from the study, or
- In the judgment of the investigator, further treatment would not be in the best interest of the patient.
- Pregnancy: Pregnant participants will continue to be followed for the duration of the pregnancy.

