## 11. STATISTICAL CONSIDERATIONS

### 11.1 Primary Endpoint

This is a 2-stage clinical trial. In the first stage, toxicity will be the primary endpoint. In the second stage (phase II component), the primary endpoint will be the locoregional progression free survival (PFS) at 1 year. Toxicities will also be evaluated during the second stage using continuous Bayesian monitoring as described below.

Sample size for the primary objective: 11 evaluable patients (stage 1); 31 evaluable patients (stage 2)

First stage: 11 evaluable patients. The safety-evaluable population for stage 1 consists of all patients who either complete the treatment regimen or withdraw from study by reason of toxicity.

Toxicities due to EGFR AS in our previous phase I trial were negligible, and consisted of grade 1 injection site pain and swelling. Because we will combine EGFR AS with radiation and cetuximab in the proposed clinical trial, a separate safety evaluation will be conducted. In the first stage (safety component), 11 patients will be treated and observed for serious adverse events (SAEs) that are due to EGFR AS (possibly, probably, or definitely), not cetuximab or radiation. In the first stage, after three (3) subjects are enrolled and have received all EGFR AS injections, there will be a two-week waiting period to assess adverse events. After the two-week period, additional subjects may be enrolled. Eligible patients will include stage IV or recurrent patients who would not be eligible for the subsequent study of efficacy, and their accrual to study is only for the assessment of safety. We seek to rule out an SAE rate of 20% or greater due to EGFR AS. If no grade 3/4 toxicities due to EGFR AS are observed among 11 patients, then an upper 90% confidence bound for the SAE rate is less than 20%.

Second stage (phase II component): 31 evaluable patients. The efficacy-evaluable population consists of all patients who complete the treatment regimen.

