### **Total sample size**

A total of 42 evaluable patients will be accrued to study.

Eleven patients will be treated in the first stage, which will assess the safety of the combination. Patients failing to complete treatment for reasons other than toxicity will be replaced.

In the second stage, 31 efficacy-evaluable patients will be enrolled, provided safety is acceptable.

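### Stage 1 evaluability does not require an EGFR AS injection, so a patient never exposed to it could count among the 11 and leave the 20% exclusion narrowly unsupported (minor)

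*Combined protocol and SAP*

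**What the plan says.** Section 11.1 of the combined protocol and SAP makes toxicity the primary endpoint of stage 1 and states the aim: "We seek to rule out an SAE rate of 20% or greater due to EGFR AS". The events counted are those possibly, probably or definitely due to EGFR AS; events due to cetuximab or radiation do not count. If none is seen in 11 patients, the section concludes that "an upper 90% confidence bound for the SAE rate is less than 20" percent.

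The denominator is defined separately: "The safety-evaluable population for stage 1 consists of all patients who either complete the treatment regimen or withdraw from study by reason of toxicity". Under Total sample size the replacement rule is: "Patients failing to complete treatment for reasons other than toxicity will be replaced".

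Three other sections determine who can enter that denominator:

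- Section 5 schedules the injections "starting 2 weeks prior to radiation and after cetuximab is administered", so the cetuximab loading dose comes before the first injection.
- Section 7.2 says: "Cetuximab should be immediately and permanently discontinued in patients who experience severe (Grade 3 or 4) infusion reactions".
- Section 7.8 lists among the criteria for removal from study: "Unacceptable adverse event(s) as defined in dose modification or other unacceptable AEs". It does not limit this to events due to EGFR AS.

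**The concern.** The numerator is restricted to EGFR AS events, but the denominator is not restricted to patients who received EGFR AS. A patient who has a grade 3 or 4 reaction to the loading dose and is removed from study has withdrawn for toxicity. That patient is evaluable under 11.1, is not replaced under Total sample size, and cannot have an EGFR AS event. The patient enters the calculation as evidence that EGFR AS is safe while carrying no information about it.

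The sample size has no spare patient to absorb this. If it happened once, the 11.1 claim of an upper bound below 20% would rest on 10 exposed patients. These patients are accrued only to assess safety, and the 20% exclusion is the one quantitative safety criterion stated for stage 1.

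**Working it through.** **Inputs.** Number evaluable 11, rate to exclude 20%, confidence 90%, zero events (all 11.1). Serious infusion reactions with cetuximab plus radiation: 3% (section 1.4, list of serious reactions; Table 2 gives the same figure for grades 3 and 4). The documents do not give the share at the loading dose, or the share that would lead to withdrawal from study. Both are assumptions below.

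**Step 1: reproduce the plan's figure.** With zero events in n patients, the exact one-sided upper 90% bound is 1 − 0.10^(1/n). For n = 11 it is 18.9%, below 20% as stated. The plan does not say whether its bound is one-sided, but only that reading reproduces it. The upper limit of a two-sided 90% interval would be 1 − 0.05^(1/11) = 23.8%.

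**Step 2: is there slack?** The smallest n with 0.8^n ≤ 0.10 is ln 0.10 / ln 0.80 = 10.32, rounded up to 11. There is none.

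**Step 3: remove unexposed patients from the 11.**

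| Exposed patients, zero events | Upper 90% bound | Chance of zero events if the true rate is 20% (0.8^n) |
|---|---|---|
| 11 | 18.9% | 8.6% |
| 10 | 20.6% | 10.7% |
| 9 | 22.6% | 13.4% |

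One unexposed patient moves the bound just past 20%.

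**Step 4: how likely is that?** Let p be the probability that a patient is removed for toxicity before any injection. The chance of at least one such patient in 11 is 1 − (1 − p)^11. Suppose that every severe loading-dose reaction leads to withdrawal, and that all, half or a quarter of the 3% occur at that dose.

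| p | At least one of 11 unexposed |
|---|---|
| 3% | 28% |
| 1.5% | 15% |
| 0.75% | 8% |

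**Step 5: effect on the stage 1 rule before any data are seen.** If the true EGFR AS rate in exposed patients is 20% and patients are independent, each of the 11 is event-free with probability p + 0.8(1 − p). The chance of zero events in 11 is (0.8 + 0.2p)^11:

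- p = 0: 0.800^11 = 8.6%
- p = 1.5%: 0.803^11 = 9.0%
- p = 3%: 0.806^11 = 9.3%

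It reaches 10% when 0.8 + 0.2p = 0.10^(1/11) = 0.811, that is at p of about 5.6%, nearly twice the 3% ceiling.

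**The case against.** **The wording may already imply exposure.** Section 11.1 says that 11 patients will be treated and observed for EGFR AS events, and Total sample size says that stage 1 assesses the combination. A patient with no injection was not treated with the combination. This is a fair reading and may be what was meant. But treated is not defined, whereas evaluable is, and that definition does not mention injections. The only stage 1 text that requires injections is the two-week pause after the first three subjects, which governs enrolment.

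**The 28% is a ceiling.** This stands. Section 6 notes that some first severe reactions came at later infusions. Section 5.1 calls for premedication before the first dose, and section 3.2 excludes patients with a prior severe infusion reaction to a monoclonal antibody. Section 7.2 ends cetuximab, not study participation; removal under 7.8 is a further decision.

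**Stronger readings that the documents do not support.**

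- A reader might infer that every early stop for cetuximab or radiation toxicity empties the denominator, and take the 14 of 208 discontinuations in section 1.4 as the rate. Those stops could come at any time. Radiation starts two weeks after the first injection, so a patient who stops for radiation toxicity would normally have had injections. For exposed patients the bound holds for the regimen as delivered.
- A reader might infer that stage 1 passes a 20% rate more than 10% of the time. Averaged over the chance of an unexposed patient, it does not.
- A reader might infer that stage 2 opens automatically on the bound. The abstract and Total sample size make it depend on the regimen being judged safe. Quarterly DSMB review (section 6.4) would probably bring to light a patient removed at the loading dose.

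**Conclusion.** The point holds as a narrow gap in a definition, of minor weight. Read literally, 11.1 and Total sample size together let a patient with no EGFR AS injection occupy one of 11 places. If that happened once and no event was seen, the claim of a bound below 20% would be wrong by a small margin: the bound is 20.6% for the 10 patients who were exposed.

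The case is unlikely. The 28% upper figure needs both assumptions in step 4 at their extreme; if either is relaxed, the chance falls. Before data, the design keeps its intended error rate at any p up to about 5.6%. The fault therefore lies in what could be reported after a particular course of events. The choice of 11 is sound, and the oversight of the trial is not in question.

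**What to change.** In 11.1, replace the stage 1 definition with wording such as:

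> The stage 1 safety-evaluable population is all patients who receive at least one EGFR AS injection and who then complete treatment or withdraw because of toxicity. Patients who receive no EGFR AS injection are reported and replaced.

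Under Total sample size, add that stage 1 patients with no EGFR AS injection are replaced whatever the reason. The present rule for patients who stop for reasons other than toxicity is unchanged, and it still replaces some exposed patients.

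No EGFR AS event can be lost, because a patient without an injection cannot have one, and the cetuximab reaction is still reported. At p = 3%, expected enrolment to reach 11 exposed patients is 11 / 0.97 = 11.34, or about 0.3 extra patients on average, and fewer at lower p. At the 1–2 patients per month in section 11.3, one replacement takes about half a month to a month.

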The efficacy and safety of cetuximab were studied in combination with radiation therapy in a randomized, controlled trial of 424 patients with locally or regionally advanced squamous cell carcinoma of the head and neck versus radiation alone. In a multicenter controlled clinical trial, 424 patients with Stage III/IV SCC of the oropharynx, hypopharynx, or larynx with no prior therapy were randomized 1:1 to receive cetuximab plus radiation therapy (211 patients) or radiation therapy alone (213 patients). Stratification factors were Karnofsky Performance Status (60-80 versus 90-100), nodal stage (N0 versus N+), tumor stage (T1-3 versus T4 using American Joint Committee on Cancer 1998 staging criteria), and radiation therapy fractionation (concomitant boost versus once-daily versus twice daily). Radiation therapy was administered for 6-7 weeks as once daily, twice daily, or concomitant boost. The planned radiation therapy regimen was chosen by the investigator prior to enrollment. For patients with  $\geq$ N1 neck disease, a post-radiation therapy neck dissection was recommended. Starting 1 week before radiation, cetuximab was administered as a 400 mg/m^2 initial dose, followed by 250 mg/m^2 weekly for the duration of radiation therapy (6-7 weeks). All cetuximab-treated patients received a 20 mg test dose on Day 1. Cetuximab was administered 1 hour prior to radiation therapy, beginning week 2. Of the 424 randomized patients, 80% were male and 83% were Caucasian. The median age was 57 years (range 34-83). There were 258 patients enrolled in US sites (61%) and 166 patients (39%) in non-US sites. Ninety percent of patients had baseline Karnofsky Performance Status 80% or greater; 60% had oropharyngeal, 25% laryngeal, and 15% hypopharyngeal primary tumors; 28% had AJCC T4 tumor stage. The patient characteristics were similar across the study arms. Fifty-six percent of the patients received radiation therapy with concomitant boost, 26% received once-daily regimen, and 18% twice-daily regimen.

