#### Duration of Therapy

Each patient will receive up to 7 weekly treatments. Treatment may be discontinued earlier if there is no identifiable tumor, a patient withdraws from study, develops intolerable toxicities, or their disease progresses (see section 7.8).

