## 9.4 Study Parameters Table

	Baseline	During treatment and 2 weeks post RT	10 +/- 2 weeks after RT	Off therapy Follow-Up 
Study treatment (See Section 5)		X	X	
History and physical exam	X	X 	X	X
Height	X			
Weight	X	X 	X	
Vital signs	X	X 		
Toxicity assessment		X	X	X
Performance Status	X	X 	X	
CBC, Differential, Platelets 	X	X 	X 	
Creatinine, Electrolytes (K + , Na + , Cl  , CO 2 ), Mg ++ , Ca ++	X	X 	X 	
Liver enzymes 	X	X (every 3 weeks)	X	
PT/PTT 	X			
Chest X-ray	X			
Pregnancy test 	X			
HIV status obtained via history	X			
CT or MRI of the head/neck	X		X	X 
CT of the chest	X		X	X 
Bone scan, if clinically indicated	X			
Tumor measurements 	X		X	X 
PET scan (optional) 	X		X	X
Swallowing assessment 	X			X 
Dental evaluation	X			
Tumor Biopsy and correlatives 	X	X (after 2 weeks)		
ENT evaluation/endoscopy	X		X	

1. Complete blood counts with differential and platelet count should be performed.
2. Liver function tests should include: Bilirubin, AST (SGOT), ALT (SGPT), and alkaline phosphatase. LFTs are required at least every 3 weeks during treatment.
3. All females of childbearing potential must have a negative pregnancy test done within 3 days of initiation of treatment to rule out pregnancy.
4. Tumor measurements will be made using physical examination, including endoscopic examination (clinically) and CT scans or MRI scans (radiographically). Clinical and radiographic assessments will be reported separately. Response in the primary and the neck will be reported separately as well. Tumor assessments will be performed 6-8 weeks after completion of radiotherapy. Subsequently, repeat imaging with CT scans of chest and head and neck will be performed every 3 months for 1 year and then every 6 months for a total of 3 years from the time of radiation completion. Then, CT of the chest or chest x-ray will be done on an annual basis.
5. Positron emission tomography (PET) scan or combined PET/CT scanning is optional. Results will be reported separately.
6. Swallowing assessments will be performed at baseline and 3 months post radiation completion, and if problems persist, at 12 months post radiation.

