Assuming that the prior probability of an SAE follows a beta distribution, the stopping rule is based on the updated posterior probability of an SAE. As each patient is observed for SAEs, the posterior probability, which follows a beta distribution, of SAE can be calculated. If at any time during the trial the posterior probability is  $\geq 0.80$  that the rate of treatment-related grade 3/4 mucositis exceeds 56%, the study will be suspended pending review by Data and Safety Monitoring Committee (DMSC). Similarly, if the posterior probability is greater than 0.80 that the rate of treatment-related grade 3/4 radiation dermatitis exceeds 23%, the study will be suspended for review by the DSMC. To permit continuous monitoring of SAEs, a table (see below) based on the cumulative number of patients experiencing SAEs at any point during the trial can be used to signal when the study should be suspended and reviewed by the DSMC.

**Table 6 Number of Patients Observed to Have Treatment-Related SAEs and Corresponding Posterior Probabilities Needed to Suspend the Study in Phase II**

Patients	Treatment-Related Grade 3/4 Mucositis		Treatment-Related Grade 3/4 Radiation Dermatitis	
	SAEs	Pr( $\pi \geq 0.56$ )*	SAEs	Pr ( $\pi \geq 0.23$ )
4	---	---	4	.825
5	---	---	4	.804
6	6	.814	5	.861
7	7	.848	5	.843
8	8	.877	5	.823
9	8	.832	5	.802
10	9	.862	6	.858
11	9	.815	6	.840
12	10	.848	6	.821
13	11	.875	6	.801
14	11	.833	7	.856
15	12	.862	7	.838
16	12	.818	7	.820
17	13	.848	7	.800
18	13	.803	8	.854
19	14	.834	8	.837
20	15	.862	8	.819
21	15	.821	9	.868
22	16	.849	9	.852
23	16	.807	9	.835
24	17	.837	9	.818
25	18	.863	10	.866
26	18	.824	10	.850
27	19	.851	10	.834
28	19	.811	10	.817
29	20	.839	11	.864
30	21	.864	11	.849
31	21	.827	11	.833

\*  $\pi$  is the posterior probability of a treatment-related SAE. For example, given the observed number of patients treated and the number of patients observed with SAEs, Pr( $\pi \geq 0.56$ ) is the posterior probability that treatment-related grade 3/4 mucositis exceeds 0.56, the expected value prior to study.

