The table above presents the minimum number of patients experiencing treatment-related SAEs (i.e., those SAEs judged to be possibly, probably, or definitely related to the study regimen) that would dictate suspension of the trial in accordance with the stopping rule. For example, after the first 10 patients have completed treatment and been observed for toxicity, 9 patients experiencing treatment-related grade 3/4 mucositis, or 6 patients experiencing treatment-related grade 3/4 radiation dermatitis, would trigger trial suspension pending review by the DSMC.

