## 11.6 Additional Analyses

The data from all evaluable patients will be used in the analyses of safety (phase I and phase II), tumor response (phase II), and survival (phase II).

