### Survival

PFS will be measured from the initial date of treatment to the date of documented progression, or the date of death (in the absence of progression).

Overall survival will be measured from the initial date of treatment to the recorded date of death or for a total of 5 years follow up (See Section 12.3).

PFS and overall survival will be estimated by the Kaplan-Meier method. The corresponding median survival times (with 90% confidence limits) will be determined, as will the cumulative percentage of patients remaining progression-free at selected time points after initial treatment.

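### The stage 2 efficacy set is limited to patients who complete treatment, which drops on-treatment progressions and deaths and biases 1-year locoregional PFS upward

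*Combined protocol and SAP*

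**What the plan says.** For stage 2, section 11.1 states: "The efficacy-evaluable population consists of all patients who complete the treatment regimen". The 31 patients in the sample size are efficacy-evaluable patients, so they are counted after this filter. Section 11.6 continues with the same term: "The data from all evaluable patients will be used in the analyses of safety (phase I and phase II), tumor response (phase II), and survival". The completer set is the only evaluable set defined for phase II.

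On the endpoint, section 11.6 (Survival) says "PFS will be measured from the initial date of treatment", with documented progression, or death without progression, as the event. On stopping, section 5.2 (Duration of Therapy) says: "Treatment may be discontinued earlier if there is no identifiable tumor, a patient withdraws from study, develops intolerable toxicities, or their disease progresses". Section 7.8 also lists progression as a reason for removal from study.

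The wording on safety is mixed. The stage 1 safety set is completers plus patients who withdraw for toxicity, and section 11.1 (Total sample size) replaces those who fail to complete for other reasons. No phase II safety set is defined. The Table 6 stopping rule in section 11.4 is updated "As each patient is observed for SAEs", but its worked example applies "after the first 10 patients have completed treatment and been observed for toxicity".

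**The concern.** Entry to the efficacy set depends on something that happens after the PFS clock has started. Progression and death during treatment are failures on the primary endpoint, and they are also reasons for not completing. Removing them removes failures and no successes.

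The historical figure has no such filter: Table 1 reports 63% locoregional control at 1 year for the full arm of 211, and section 11.1 uses that 211 to derive the 68% null. Only the new data are selected.

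This is the trial's only efficacy test, on 31 patients, so a positive result near the boundary can rest on one or two excluded failures. Because completion is not defined, the choice of who counts could also be made after outcomes are known.

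**Working it through.** **Inputs.** Null 68% and alternative 83% at 1 year, hazard ratio 0.5, one-sided alpha 0.10, N = 31, 2 years of accrual plus 1 year of follow-up, exponential PFS (section 11.1). Treatment lasts 2 weeks before radiation plus 7 weeks of radiation, so 9 weeks (study schema). A 7% discontinuation rate, primarily for adverse events, with cetuximab plus radiation (section 1.4). The documents give no on-treatment progression or death rate.

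**1. The plan's own figure.** The hazards are λ0 = −ln 0.68 = 0.386 and λ1 = −ln 0.83 = 0.186. With uniform accrual, P(event) = 1 − [exp(−λ) − exp(−3λ)]/(2λ), which gives 0.526 and 0.307, or d0 = 16.3 and d1 = 9.5 expected events in 31 patients. Power = Φ{[ln(λ0/λ1) − 1.2816/√d0]·√d1} = 0.897. The stated 90% reproduces when all patients are counted from first treatment. With the hazard ratio at exactly 0.5 it is 0.880.

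**2. Events lost under the plan's model.** At the null, the share with an event in the first 9 weeks is 1 − exp(−0.386 × 9/52) = 6.46%, and 31 × 0.0646 = 2.0 patients. If a share s of these is excluded, the remaining patients' 1-year rate is 0.68/(1 − 0.0646s). I simulated the one-sided log-hazard exponential test with n = 31, 100,000 runs and the normal cut-off. The last two columns give the probability of a positive result.

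| Share of early events excluded | 1-year rate when truth is 68% | True rate 68% | True rate 63% |
|---|---|---|---|
| none | 68.0% | 0.087 | 0.018 |
| quarter | 69.1% | 0.108 | 0.023 |
| half | 70.3% | 0.129 | 0.031 |
| all | 72.7% | 0.189 | 0.054 |

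If the cut-off is calibrated to exactly 0.10 with nobody excluded, excluding all early events gives about 0.21.

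**3. Sensitivity to who fails to complete.** Let f be the non-completers' share and p their 1-year rate. The completers' rate is (0.68 − f·p)/(1 − f). As a simple binomial illustration, 25 of 31 is the smallest count that passes against 68% at 0.10, with P(X ≥ 25) = 0.090. Only the 7% has a source in the documents; 10%, 15% and every value of p are assumptions.

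| p | f = 7% | f = 10% | f = 15% |
|---|---|---|---|
| 60% | 0.102 | 0.108 | 0.120 |
| 50% | 0.119 | 0.135 | 0.168 |
| 30% | 0.158 | 0.201 | 0.299 |
| 0% | 0.234 | 0.337 | 0.571 |

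**4. One or two patients at the boundary.** Exact one-sided p against 68%: 25 of 31 gives 0.090. Restoring one excluded failure (25 of 32) gives 0.149, and restoring two (25 of 33) gives 0.224.

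**5. Stage 1.** A patient who has a qualifying event due to EGFR AS and then leaves for another reason, such as progression, is neither a completer nor a toxicity withdrawal. That patient is replaced, so the rule of no events in 11 can be met although an event occurred.

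**The case against.** - **Completion is undefined.** Injections may be fewer than seven and may be omitted for toxicity, so a reading that requires every dose is implausible. This stands as a gap in the text. It does not bring back a patient who progresses or dies during treatment.
- **Few early progressions may be documented.** Section 9.4 says "Tumor assessments will be performed 6-8 weeks after completion of radiotherapy", and no tumour imaging is scheduled during treatment. This stands, and it makes the full-exclusion row an upper case. Patients are examined weekly, however, and deaths need no imaging.
- **The direction is unknown for patients who leave for toxicity or by choice.** This stands; the documents give no outcomes for them. The upward bias from excluded progressions and deaths is unaffected.
- **The endpoint is loosely defined.** Locoregional PFS has no definition of its own, section 2 names locoregional control, and the 63% is tabulated as control. Whether the benchmark counted deaths cannot be settled from the documents. If it did not, counting deaths here would work against the new regimen. This is a separate mismatch and does not justify filtering one side.
- **The null has a margin.** It was raised from 63% to 68%, and at a true 63% a positive result stays near 0.05 even in the upper case. This limits the practical damage, but the plan's stated alpha refers to 68%.
- **The boundary example is chosen at the cut-off, with a binomial rather than the planned exponential test.** True; it shows how sensitive the result can be, not how often it would reverse.

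**Conclusion.** The concern holds. As written, the only efficacy test leaves out on-treatment failures, compares the remainder with an unfiltered historical arm, and has no all-treated analysis to fall back on. The sample size calculation itself is sound; the fault is in the analysis set.

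The upward direction for excluded progressions and deaths does not depend on a model. The size does. With constant hazard and a 9-week window, type I error at 68% is 0.11 to 0.13 if a quarter to a half of early events are lost, and 0.19 if all are. A constant hazard may overstate early events.

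That the restriction also covers response and survival is an inference from the word evaluable in section 11.6, but no other phase II evaluable set exists. The stage 1 gap follows from the text. The phase II safety set is a missing definition that sections 11.4 and 11.6 leave open to two readings.

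**What to change.** Amend section 11 as follows.

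- **Stage 2 efficacy set:** all eligible patients who receive any protocol treatment, with locoregional progression or death on treatment counted as an event from day 1. Keep N = 31 such patients, and use the same set for response and survival.
- **Completers:** report as a sensitivity analysis only. Define completion in advance, so that an injection omitted as the protocol directs is not non-completion.
- **Safety set, both stages:** all patients who receive any EGFR AS. State that the Table 6 rule uses this set.
- **Stage 1:** count a qualifying event whatever the reason for leaving, and replace only patients who leave early without one.

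The cost is one protocol amendment. The number of patients analysed stays at 31 and power at about 90% under the plan's assumptions. The estimate is likely to be slightly less favourable. No treatment or visit changes.
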